SPECIFIC AIM 1: To provide preliminary data about the efficacy of riluzole treatment in improving PTSD symptoms. *Hypothesis*: PTSD subjects treated with

riluzole (50 mg twice per day for 12 weeks) will have reduction in PTSD symptoms. To examine the efficacy of riluzole we will compare the mean change in the CAPS total score over the course of 12 weeks of riluzole treatment.

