- A. Participants: Twenty patients with a current diagnosis of PTSD or sub-threshold PTSD between the ages of 18-75 will complete the treatment phase of the study. Subjects will initially be pre-screened by phone interview and a preliminary medical record review. Eligible subjects will then be invited for an in-office visit and will complete the written informed consent process. Subjects will be thoroughly screened for inclusion and exclusion criteria as described below.
- B. Discontinuation of subjects: Subjects may be discontinued from study treatment and assessments at any time. Specific reasons for discontinuing a subject from this study are:
  - Voluntary discontinuation by the subject, who is at any time free to discontinue his/her participation in the study without prejudice to further treatment;
  - Clinical deterioration: The following are objective criteria for clinical deterioration, (1) a 35% increase in CAPS scores at any time during the study, (2) Patients with a CGI-I score ≥ 6 at any post-baseline visit, and (3) the onset of active suicidality as assessed by the study investigator or by scoring 5 or more on the item-10 of MADRS;
  - Evidence of neutropenia (ANC ≤ 1500) or other intolerable adverse reaction, or unable to tolerate study drug;
  - Transaminase levels > 5x ULN;
  - Safety reasons as judged by the investigator;
  - Stopping birth control or positive pregnancy test;
  - Evidence of illicit drug abuse (except for cannabis) or problematic alcohol use during trial;
  - Non-compliance to protocol as judged by the investigator; Subjects who do not take between 75-125% of study medication for two consecutive visits are considered non-adherent and are withdrawn from the study medication.

A subject that prematurely discontinues (i.e. stops study medication or no longer wishes to participate) will always be asked about the reason(s) for discontinuation and the presence of any adverse events. If possible, they will be seen and assessed by the investigator. Adverse events will be followed up as medically necessary.

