It is estimated that the total amount of time required by the patient to determine screening eligibility will be 7 hours. It will require one hour of time to complete each of the scheduled CAPS interviews. Repeated follow-up visits (including rating scales, blood work, urine screens, etc.) without the above cited assessments, will last for approximately 45 minutes to one hour. If necessary due to time commitments or difficulties with scheduling, some visits may take place over more than one day during the study week.

Each of the psychiatric, behavioral and cognitive assessment instruments is briefly described below.

- 1. Clinician Administered PTSD Scale (CAPS): The CAPS is a standardized clinician-rated instrument to assess the presence and severity of PTSD symptoms.
- 2. Post Traumatic Stress Disorder Checklist (PCL): The PCL is used to measure PTSD symptoms and is a self-report questionnaire that shares similar reliability with the CAPS.
- 3. The Combat Exposure Scale (CES): The CES is a self-report instrument that measures reports of wartime stressors on a 5 point Likert Scale format.
- 4. Early Trauma Inventory (ETI-SR) The ETI-SR is a self-report instrument to assess childhood trauma and includes physical, emotional and sexual abuse as well as general traumas.
- 5. Klein Loss Scale (KLS): The KLS is a self-report of parental loss or separation during childhood.
- 6. Global Perceived Early Life Stress (GPELS): The GPELS is a self-report of perceived stress during childhood.
- 7. Montgomery-Asberg Depression Rating Scale (MADRS): The MADRS is a standardized instrument to ascertain depressed mood and neurovegetative signs and symptoms of depression.
- 8. *Quick Inventory of Depressive Symptoms Self-Report* (QIDS-SR): The QIDS-SR is a patient-rated depression instrument.
- 9. Massachusetts General Hospital Antidepressant Treatment History Questionnaire (MGH-ATRQ)-This is a self-rated questionnaire used to determine treatment resistance in major depressive disorder.

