#### **Data Analysis**

Descriptive statistics will be calculated prior to statistical analysis. Distributions of quantitative variables will be assessed for normality using normal probability plots and Kolmogorov-Smirnov statistics and transformations or non-parametric methods will be used as necessary. All statistical tests will be two-sided. Uncorrected alpha level of 0.05 will be used for testing the primary hypothesis. Pairwise post-hoc comparisons and tests of secondary outcome measures will be adjusted using Holm-Bonferroni procedure. All analyses will be intent-to-treat. We will using mixed effects regression models, with time effects for the primary outcome variable (CAPS). We do not expect significant moderating effects of alcohol use comorbidity but will assess the interaction between treatment and alcohol use comorbidity and perform follow-up tests as necessary. This approach will be applied to most secondary outcome measures as well. Mixed effects regression models use all available data on each subject, are flexible in modeling the correlation structure of the data and give unbiased results under missing at random

assumptions. In addition to testing the potential moderating effect of comorbid alcohol use described above, we will also perform exploratory analyses to the assess moderating effects of depression, medication status, substance abuse, age, and gender by adding these factors one at a time to the models above and testing interactions between each potential moderator and treatment group. Effects of intermittent missing data due to noncompliance with treatment schedule can also be assessed.

Table 1. Schedule of Study Events\*\*

	1 doie 1. Senedule of Study Events											
Visit	Screeni ng a	Baselin e	1	2&3	4	5,6,&7	8	9,10,11	12	month follow- up		
Day	0	0	7	14&21	28	35,42, & 49	56	63, 70, &77	84	114		
Informed Consent b	X											
Demographics	X											
SCID / MINI	X											
C-SSRS baseline	X											
MGH ATRQ	X											
ETI-SR, KLS, GPELS, CES	X											
M-MACE	X											
Psychiatric Evaluation	X											
BP, Pulse, Resp., Wt., Temp.	X	X	X	X	X	X	X	X	X			
ECG	X											
Physical Exam	X											
СВС	X				X		X		X			
СМР	X				LFTs		LF Ts		LFTs			
Serum Pregnancy (1)/ Urine Pregnancy (2)	X(1)	X (2)			X(2)		X( 2)		X(2)			
Urinalysis	X											
Inclusion/Exclusion	X											
CAPS	X	X °				X (visit 6 only)			X	X		
MADRS	X	X	X	X	X	X	X	X	X	X		
PCL, QIDS-SR, PSWQ, PSQI, SDS, SAFTEE		X	X	X	X	X	X	X	X	X		

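### Missing at random is not secured for the CAPS-only primary model, because weekly scores outside the model trigger discontinuation; if CAPS stops there, improvement is likely overstated

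*Combined protocol and SAP*

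**What the plan says.** The primary aim (Specific Aim 1) is to "compare the mean change in the CAPS total score over the course of 12 weeks of riluzole treatment". The Data Analysis section specifies mixed effects regression with time effects for CAPS, in an intent-to-treat analysis. It supports this choice by saying that such models are "flexible in modeling the correlation structure of the data and give unbiased results under missing at random" assumptions. No other scale is named as a covariate or joint outcome in the primary model. The only missing-data check mentioned is optional and concerns gaps, not drop-out: "Effects of intermittent missing data due to noncompliance with treatment schedule can also be assessed".

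Table 1 schedules CAPS at screening, at baseline (a conditional repeat), at visit 6 (day 42), at visit 12 (day 84) and at the one-month follow-up (day 114). MADRS, CGI-S/I and PCL are scheduled at every weekly visit. Of the PCL, section 11.C.3 says: "The PCL is used to measure PTSD symptoms and is a self-report questionnaire that shares similar reliability with the CAPS".

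Section 11.B gives three criteria for clinical deterioration. The first is a 35% rise in CAPS. The second is "2) Patients with a CGI-I score ≥ 6 at any post-baseline visit". The third is active suicidality, judged by the investigator or by a score of 5 or more on MADRS item 10. Section 12 (Suicidal Ideation and Imminent Harm) repeats the CGI-I and MADRS item 10 rules.

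**The concern.** Missing at random is a statement about missingness given the data the model contains. A model that holds only CAPS can adjust only for recorded CAPS. A subject lost before week 6 gives it nothing but a pre-treatment score. Before visit 6 no post-baseline CAPS is scheduled, so on the planned schedule any score-triggered exit in that period must come from CGI-I or MADRS item 10, which the model does not see.

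These rules act in one direction: they remove subjects who are getting worse. If CAPS ends when they leave, the remaining CAPS values look better than those of the whole treated group. The trial has one arm, so no control group shares and offsets this. The result at risk is the only primary estimate, and section 6 says the data will inform larger studies.

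**Working it through.** **1. Planning figures.** Section 7 gives about 50 enrolled for 20 completers, so 1 − 20/50 = 60% are lost to screening failure and drop-out together. Drop-out alone cannot be recovered. If it were 20%, 30% or 40% of those dosed, the number dosed would be 20/0.8 = 25, 20/0.7 = 29 or 20/0.6 = 34. The documents state no SD, trigger rate, power or bias figure, so there is no planned value to reproduce.

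**2. Does CAPS continue after discontinuation?** The passages disagree.
- Towards yes: section 11.C.3 asks willing subjects who stop the drug to keep attending evaluations, says they are told this at consent, and gives safety monitoring as the reason.
- Towards no: section 11.B allows discontinuation from assessments as well as treatment. Section 12 says subjects who meet the CGI-I or MADRS item 10 rule leave the study. Section 11.C.3 also counts non-adherent patients as dropouts in an analysis that Data Analysis calls intent-to-treat.

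**3. Simulation (all values assumed; 400,000 subjects per scenario).** Severity in week t is L(t) = b + s·t/12 + e(t), with b ~ N(40, 9²), s ~ N(−8, 10²), and e(t) autoregressive with SD 5 and lag-one correlation 0.7. CAPS is L plus error of SD 3, seen at weeks 0, 6 and 12. The SD of 12-week change is √(10² + 2·5²·(1 − 0.7¹²) + 2·3²) = 12.9. A weekly CGI-I-type score is 4 + [L(t) − L(0)]/k + noise of SD τ. Withdrawal occurs at the first score at or above a cut-off c. The CAPS-only mixed model has free visit means and free covariance, fitted by maximum likelihood. Entries are estimated 12-week change, with the full-data value in brackets.

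| c, τ, k | Meeting rule | CAPS-only, all withdrawn lost | CAPS-only, half retained | Weekly trigger score added, all lost |
|---|---|---|---|---|
| 6.5, 0.4, 9 | 2% | −8.21 (−8.01) | −8.12 (−8.02) | −8.01 |
| 6, 0.4, 9 | 5% | −8.54 (−7.97) | −8.30 (−8.03) | −7.97 |
| 5.5, 0.3, 8 | 14% | −9.55 (−7.96) | −8.70 (−8.00) | −7.96 |
| 5.5, 0.7, 12 | 23% | −9.78 (−8.00) | −8.76 (−7.99) | −8.00 |
| 5.5, 0.7, 7 | 31% | −11.03 (−8.02) | −9.21 (−8.00) | −8.02 |
| 5.5, 0.7, 5 | 37% | −11.87 (−8.00) | −9.50 (−8.02) | −7.98 |

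Overstatement with all withdrawn lost runs from 8.21 − 8.01 = 0.20 to 11.87 − 8.00 = 3.87 points. With half retained it runs from 8.12 − 8.02 = 0.10 to 9.50 − 8.02 = 1.48. With everyone retained it is zero in each scenario. With 30% drop-out unrelated to symptoms, the CAPS-only estimate was −8.00 against −8.00.

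The CAPS-only model does help a little. At 31%, completers alone gave −12.35, so it removed (12.35 − 11.03)/(12.35 − 8.02) = 1.32/4.33, or 30%, of the completer bias.

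**4. Which auxiliary scores?** In a separate run with drop-out driven by CGI-I, true change about −8 and 30% lost, CAPS-only gave −10.1. Adding weekly PCL gave −9.0 to −9.5. Adding visit-specific weekly CGI-I as well gave −8.2.

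A joint CAPS–PCL model with an unscaled shared random intercept and slope did worse. With a separate clinician-type rating driving drop-out and PCL random effects correlated 0.7 with those of CAPS, CAPS-only gave −8.76, the joint model −8.63 and full data −7.99. It removed 0.13/0.77, or 17%, of the bias. With PCL itself driving drop-out but on a scale 1.5 times that of CAPS, it over-corrected to about −7.7 (full data −8.0).

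**5. Small sample.** With 33 subjects and 30% lost, including the trigger scores lowered the root mean squared error from about 2.8 to between 2.1 and 2.3.

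**The case against.** A reader might infer that missing at random is false by the protocol's own rules and that the CAPS improvement is overstated as a matter of fact. The documents do not support that, for five reasons.

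- The sentence in Data Analysis states a general property of mixed models. It does not assert that the condition holds in this trial.
- The bias needs CAPS to be missing after discontinuation, and section 11.C.3 plans continued evaluation of willing subjects. With full retention there is no bias.
- Not every rule lies outside the model. The 35% CAPS criterion acts on the modelled outcome when it uses a recorded CAPS. Transaminases, neutropenia and pregnancy need not track symptoms, and intolerance or non-adherence matters only if related to unseen CAPS.
- CAPS is also taken at screening and at day 114, although day 114 falls after the 12-week endpoint.
- No trigger or drop-out rate is given, and the 50-for-20 figure mixes screening failure with drop-out.

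All of this stands against certainty and against any fixed size, but it does not remove the point. Continued evaluation covers only those willing, other passages contradict it, and CAPS collected from subjects classed as dropouts might not be analysed. With half of the withdrawn subjects retained, some bias remained in every scenario tabulated.

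**Conclusion.** The point holds in conditional form. As written, the plan does not secure missing at random given CAPS alone. If CAPS is lost at discontinuation, the likely direction of bias is towards benefit.

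Under the assumed values the size is about 0.2 points at 2% withdrawn by the score rules and 2 to 4 points at 30% to 37%, against a true change of −8. It is zero under full retention or symptom-unrelated drop-out. These figures rest on an assumed severity model and a CGI-I-type trigger; MADRS item 10 was not simulated separately. They show that the effect can matter, not that it will.

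A change is worth making because the scores that would make the assumption more plausible are already collected weekly. Including them helps only as far as recorded scores explain who leaves.

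**What to change.** 1. Reconcile sections 11.B, 11.C.3 and 12 on whether CAPS is assessed and analysed after study drug stops, including what it means to class non-adherent patients as dropouts. Use every CAPS collected in the intent-to-treat analysis.
2. Handle missing week-6 and week-12 CAPS by multiple imputation, or by a joint model with scale-specific loadings. Include the visit-specific weekly scores already collected: the triggers CGI-I and MADRS (with item 10), and PCL. Do not rely on a PCL-only model with an unscaled shared random intercept and slope.
3. Report the CAPS-only mixed model alongside as a sensitivity analysis.

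The cost is a text reconciliation, revised analysis wording and modest extra programming. Step 2 needs no new data. The downside is a larger model, which at this sample size must be kept small or regularised.

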**6. Significance of proposed research:** Our proposed study is the first to examine the effect and feasibility of riluzole treatment for PTSD. Data from this pilot study will inform the design of future larger double-blind controlled studies. For e.g., if PTSD veterans showed full early response to riluzole following 1-4 weeks, this will affect the design of future definitive (likely multisite) studies. While placebo-controlled studies are standard for FDA approval and definitive clinical trials confirming efficacy, an open label approach is appropriate for pilot studies seeking early signals of efficacy and optimal treatment regimen. Pilot open label studies are essential for early phase of drug development.

**7. Experimental subjects**: We anticipate approximately 20 male and female subjects with PTSD, between the ages of 18-75 years, to complete all study procedures. In order to account for screenings failure and subject drop outs, and retain a sample of 20 subjects completing the treatment phase, approximately 50 eligible subjects will be enrolled.

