- **9. Selection**: Subject eligibility will first be assessed via telephone screening and if records are available, by a preliminary medical record review. If the subject seems to be a likely candidate for inclusion in this protocol, he or she will be evaluated for study eligibility in person. Telephone screens will occur by experienced research personnel adept with this process. Following a face-to-face evaluation and discussion with the research team, an experienced study investigator will determine suitability for enrollment.
- 10. Recruitment: Subjects will be recruited through flyers, public advertisement (newspaper, radio, internet posting), by word of mouth, contact with community service groups, our local IRB-approved screening protocol (KW0003), and clinics and local treatment facilities (e.g., VA Hospital, Community-Based Outpatient Clinics, local private practices). Subjects will be identified via their response to advertisements and/or internal recruiting through the research clinics. Subjects will be asked to call us at the number provided on the flyers if they are interested in participating in the research study. Subjects will be contacted for follow-up appointments via the most convenient means and personal preference, e.g. telephone. All available research staff is responsible for recruiting potential subjects.
- 11. Research Plan: This study will be conducted at the VA Hospital, West Haven, CT.

Overview: This is a diagnosis-informed study designed to provide preliminary data regarding the efficacy and tolerability of riluzole to treat symptoms of PTSD. Subjects diagnosed with PTSD will receive riluzole, 50 mg taken twice daily (BID) for 12 weeks. PTSD subjects will be followed closely on a weekly basis and their liver function and pregnancy tests will be repeated (see Table 1).

Dosing: Following confirmation of eligibility, the dosing regimen for the first week of study medication is 50 mg twice a day (BID). Subjects who are unable to tolerate the study medication will be allowed to take a lower dose. For these subjects, the dose may be lowered to 50 mg taken once a day (QD). Subjects who are unable to tolerate the once a day 50 mg (QD) dosing regimen will be discontinued from the study. Riluzole should be taken 1 hour before or 2 hours after a meal to avoid food-related decreases in bioavailability.

A schedule of the study events is provided in Table 1.

Figure 1. Study Design

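### Five moderators are to be tested for interaction with a treatment group that does not vary in this one-arm trial; the estimable term is moderator-by-time

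*Combined protocol and SAP*

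**What the plan says.** The trial has one arm. Section 11 (Research Plan, Overview) states: "Subjects diagnosed with PTSD will receive riluzole, 50 mg taken twice daily (BID) for 12 weeks". Section 6 (Significance) says that "an open label approach is appropriate for pilot studies seeking early signals of efficacy" and leaves controlled comparison to later studies. Specific Aim 1 defines the efficacy question within subjects: "we will compare the mean change in the CAPS total score over the course of 12 weeks of riluzole treatment".

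The Data Analysis section then makes four statements that bear on this point:

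- The base analysis uses "mixed effects regression models, with time effects for the primary outcome variable (CAPS". No group term is named.
- For comorbid alcohol use, the investigators "will assess the interaction between treatment and alcohol use comorbidity". The plan does not say whether treatment here means a group or time on treatment.
- The next sentence reads: "This approach will be applied to most secondary outcome measures as well".
- Five further factors are to be explored "by adding these factors one at a time to the models above", and the tests are described as "testing interactions between each potential moderator and treatment group".

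**The concern.** A moderator-by-group interaction asks whether the difference between groups depends on the moderator. With one group there is no such difference, so the five tests as worded correspond to no quantity the data can supply. The analyst would have to choose a substitute term after the data are in hand.

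The substitute may not be a sensible one. Software commonly drops a redundant column and still prints a coefficient for the moderator. That coefficient describes how subgroups differ in CAPS level. A subgroup that is simply more severe at every visit could then be reported as responding differently to riluzole. Section 6 says this pilot will inform later trials, so such a reading could carry into their design.

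**Working it through.** The plan gives no figure for the moderator tests, so there is nothing to reproduce. The question is whether the stated term can be estimated, which the rank of the fixed-effects design matrix answers.

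**Inputs.** One arm, so G = 1 for everyone (section 11). CAPS at baseline, week 6 and week 12, plus the one-month follow-up in a second run (Table 1). Table 1 footnote c makes the baseline repeat conditional on investigator discretion or on 4 or more weeks having elapsed, so baseline here means the last pre-treatment CAPS. Categorical time is an assumption; the plan says only that there are time effects. About 20 completers and about 50 enrolled (section 7).

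**Model with treatment group.** With W6 and W12 as visit indicators and M as the moderator:

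E(CAPS) = b0 + b1·W6 + b2·W12 + g·G + d·M + h·(M×G)

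Setting G = 1 gives

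E(CAPS) = (b0 + g) + b1·W6 + b2·W12 + (d + h)·M

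There are two exact dependencies: G equals the intercept column, and M×G equals M. The rank is 6 − 2 = 4. Only the sum d + h is estimable; neither d nor h is. The dependencies do not involve the time columns, so another coding of time does not remove them.

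| Fixed effects | Columns | Rank | Interaction estimable? |
|---|---|---|---|
| Time, G, M, M×G (3 visits) | 6 | 4 | No |
| Time, M, M×time (3 visits) | 6 | 6 | Yes |
| Time, M, M×time, plus G, M×G, M×G×time (3 visits) | 10 | 6 | Only as M×time |
| Time, G, M, M×G (with follow-up) | 7 | 5 | No |
| Time, M, M×time (with follow-up) | 8 | 8 | Yes |

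The first two models and their follow-up versions were checked with a binary moderator and with a continuous one (ages spread over 18–75). The ranks were the same at n = 20 and n = 50, so more subjects would not help.

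**What the leftover coefficient measures.** By generalised least squares with complete data, the estimate of d + h is a weighted average of the moderator differences at the three visits.

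- Equal within-subject correlation: weights 1/3, 1/3, 1/3.
- First-order autoregressive correlation r: weights proportional to 1, 1 − r, 1. At r = 0.6 these are 1, 0.4, 1, with total 2.4, giving 0.417, 0.167, 0.417.
- In both cases the weights sum to 1, which makes it a comparison of level.
- The baseline-to-week-12 change contrast has weights −1, 0, +1, which sum to 0.

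If a subgroup is k points higher at all three visits, the leftover coefficient is k and the change contrast is k − k = 0. If the subgroups are equal at baseline and differ by k/2 at week 6 and k at week 12, the leftover coefficient under equal correlation is (0 + k/2 + k)/3 = k/2, while the change contrast is k.

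**Precision of the estimable term.** Assume a binary moderator, change scores, two-sided 0.05, 80% power and a normal approximation. The smallest detectable difference in change, in SD of change, is (1.960 + 0.842) × √(1/n1 + 1/n2). With 20 subjects it is 2.802 × √(1/10 + 1/10) = 1.25 for a 50:50 split and 2.802 × √(1/5 + 1/15) = 1.45 for 25:75. With 50 analysed it is 0.79 and 0.91. The splits are assumptions, and 50 is an upper bound because that enrolment figure also covers screening failures and drop-outs.

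**The case against.** The plan writes out no design matrix. It adds the factors to models that contain time, under an aim defined as CAPS change, so a competent analyst would probably fit moderator-by-time anyway. If group is added to that model together with its products, the group terms are redundant and moderator-by-time remains (rank 6 of 10 columns). On this view the harm needs one particular literal model followed by a misreading. That is a fair account of the likely intent and it limits the severity. It does not make the stated term estimable, and the plan nowhere says that time is meant.

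Other points stand in part:

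- The alcohol sentence follows directly on the time-effects sentence and reads naturally as change over time on treatment, which is estimable. There the need is for clarification. Whether the undefined term carries over to the secondary outcomes is likewise uncertain.
- The weights above illustrate a possible misreading and depend on complete data and an assumed correlation. The non-estimability result does not depend on them.
- That one arm cannot separate a modified drug effect from natural course, regression to the mean or expectancy is true of any single-arm study. It bears on how the corrected results are labelled, and it is not caused by the wording.
- Figure 1 (Study Design) was not visible for this review. The text consistently describes one arm. The reduction to once-daily dosing in section 11 is a post-baseline response to intolerance and is never defined as a group.

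**Conclusion.** The concern holds. As written, the five exploratory interactions cannot be estimated at any sample size, because treatment group is constant (rank 4 of 6 with three visits, 5 of 7 with follow-up). The moderator-by-time term that was probably intended can be estimated (6 of 6 and 8 of 8). The alcohol test shares the fault only if its treatment term means group.

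The conclusion rests on the single arm described in the text. It does not rest on the number of subjects, the type of moderator or the coding of time. Severity is minor: the five tests are labelled exploratory and the primary test of CAPS over time is untouched. Even when corrected, the terms will be imprecise and will show who changes more while on riluzole, without attributing the difference to the drug.

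**What to change.** In the Data Analysis section, replace the references to treatment and treatment group in the moderator sentences with moderator-by-time interactions. Suggested content:

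> For each factor in turn, the factor's main effect and its interaction with time will be added to the CAPS model. The contrast of interest is the difference between factor levels (per unit for age) in CAPS change from baseline to week 12, reported with a 95% confidence interval. Because there is no control arm, these results will be described as predictors of CAPS change during riluzole treatment.

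Use the same term for comorbid alcohol use, keeping that test's separate status as the plan has it, and say whether it also applies to the secondary outcomes. State whether time is categorical or linear.

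The cost is a few reworded sentences. No new data, visits or tests are needed.
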